4.2 Close-down Plan23
5. References25
6. Appendix Dummy Tables

6.1Conservative Management Costs	28
6.2 Pharmacological interventions	41
6.3 Healthcare Resources	45
6.4 Time and Travel Questionnaire	50

1. A summary of the protocol

CONFORM-OH is funded by the National Institute of Health Research (NIHR) Health Technology Assessment Programme. The study is a randomised controlled trial with an embedded economic evaluation. This randomised controlled trial aims to evaluate the clinical and cost-effectiveness of the following three strategies in the treatment of Orthostatic Hypotension (OH):

- Conservative management (non-pharmacologic treatments)
- Conservative management plus Fludrocortisone
- Conservative management plus Midodrine.

OH is a common and disabling condition that significantly reduces blood pressure (BP) on standing upright ⁽¹⁾. Older people and individuals with chronic diseases are more likely to have Orthostatic Hypotension ⁽²⁻³⁾. A decline in standing BP causes a decrease in perfusion in the brain, causing a range of non-specific symptoms, including dizziness, headache, nausea, fatigue and visual disturbance; at its most severe, it can cause falls and syncope (fainting) ⁽⁴⁾. People with Orthostatic Hypotension have an increased risk of stroke, cognitive impairment and all-cause mortality and they can experience a significant reduction in quality of life ^(5, 6,7.8).

There is a significant unmet clinical need due to insufficient evidence supporting Orthostatic Hypotension management ⁽⁹⁾. Researchers have consistently described systematic reviews and meta-analyses of this evidence base as poor quality with current treatment recommendations based on expert opinion. They recommended more rigorous evaluation to guide clinical practice ⁽¹⁰⁻¹⁴⁾.

The cost of OH medication is modest, but the consequences of successful treatment and the costs of managing side effects are unknown. No high-quality economic evaluations are directly applicable to the NHS comparing these interventions. Thus, the NHS has insufficient evidence about which Orthostatic Hypotension therapy represents a good use of scarce NHS resources. The scarcity of information about the economics of Orthostatic Hypotension therapy results from the lack of evidence on the relative cost-effectiveness of Fludrocortisone and Midodrine.

The CONFORM-OH aims to provide evidence to guide the treatment of Orthostatic Hypotension.

2. Outline of economic analysis

The key objective of this economic plan is to outline how an economic evaluation will be carried out as part of the CONFORM-OH trial. It was planned that the study will include a within-trial cost-utility analysis with a longer-term model-based extrapolation to estimate the incremental cost per quality-adjusted life-years (QALYs). QALYs will be derived based on responses to the EQ-5D-5L. The rationale behind using a model-based analysis and a trial-based analysis is that the results of the within-trial study might indicate that a treatment strategy for Orthostatic Hypotension is not cost-effective. Still, it is plausible that extrapolation might change this conclusion. However, the converse can also occur, where a strategy initially found to be cost-effective becomes cost-ineffective when longer-term costs and effects are considered. Therefore, an economic evaluation model was planned to extrapolate cost and QALYs beyond the 12-month trial follow-up period. Section 4 presents further details of this analysis.

The perspective of the CONFORM trial is that of the UK National Health Service (NHS) and Personal and Social Services (PSS). Healthcare resource use will be the main cost of this economic evaluation. The economic assessment will calculate the average cost to the NHS of interventions, conservative management plus Fludrocortisone and conservative management plus Midodrine. We will also calculate the average costs of the comparator, conservative management. A sensitivity analysis will explore a broader perspective considering the price falling on individuals or their families/carers. Within the sensitivity analysis, this cost will include direct, e.g., out-of-pocket costs of any medications or therapies purchased and indirect costs such as time off, paid work and travel, and costs to the NHS.

The within-trial economic evaluation was planned to report the following economic outcomes:

- NHS cost of managing individuals with Orthostatic Hypotension over 12 months.
- Direct and indirect costs fall on individuals who suffer from Orthostatic Hypotension and their families/carers over 12 months.

- QALYs estimated based on responses to the EQ-5D-5L administered at baseline, three, six, and 12 months post-randomisation.
- The incremental cost-effectiveness ratio (ICER) is the incremental cost per QALY gained for a more effective but more costly intervention than a less costly but less effective one.

The model-based economic evaluation was planned to report the following economic outcomes:

- NHS cost of managing individuals with Orthostatic Hypotension over the estimated patient lifetime.
- Direct and indirect costs fall on individuals who suffer from O and their families/carers over the estimated patient lifetime.
- QALYs estimated based on responses to the EQ-5D-5L over the estimated patient lifetime.
- The incremental cost-effectiveness ratio (ICER) is the incremental cost per QALY gained for a more effective but more costly intervention than a less costly but less effective one.

CONFORM-OH has closed early as recruitment did not reach planned targets. This health economics analysis plan reports the originally planned Within-Trial Analysis (section 3); the plan for the economic analysis of the data given the early termination is reported in section 4.

3. Within – Trial analysis

Using the cost and effectiveness data derived from the trial allows the estimation of Fludrocortisone's cost-effectiveness compared to Midodrine and Conservative Management. The economic analysis will be an intention-to-treat (ITT) analysis.

3.1 Description of management strategies

The CONFORM protocol version 2.0 provides a more detailed description of the OH strategies. The CONFORM study is analysing the following management strategies.

- Conservative management In this study, non-pharmacologic therapy is standard first-line care and represents the control arm of the trial.
- Fludrocortisone with conservative management -The typical starting dose will be 100 micrograms, and the highest amount used in this study will be 400 micrograms. The PI has judged participants to be frailer and may have a lower starting dose of 50 micrograms.
- Midodrine with conservative management The recommended dose range is 2.5 milligrams three to 10 milligrams three times a day. Within this study, lower frequencies and doses may also be accepted.

The duration of follow-up for the three arms is 12 months from randomisation.

3.2 Format of the incremental analysis

Table 1 will present all analysis costs, QALYs, and the ICER. Treatments A-C do not a priori represent any of the interventions. Instead, the treatments are ordered from least costly (treatment A) to most costly (treatment C). The table assumes that treatment B is more costly and more effective than treatment A and that treatment C is more costly and more effective than treatment B. Thus, the calculation of ICERs compares treatment B to treatment A and treatment C. Should one or two treatments be more costly and no more effective (and possibly less effective), these treatments will be considered dominated and dropped from the analysis. For example, suppose treatment B is more costly and no more effective than treatment A. I. In this case, treatment A will dominate B. In this situation, the ICER would be calculated for treatment C compared with treatment A (assuming treatment C is more effective than treatment A).

Table1:Incremental cost-effectiveness of conservative management vsFludrocortisone with conservative management vs Midodrine with
conservative management

Treatment Arm	Costs	Incremental Costs	Effects	Incremental Effects	ICER
A	A				
В	В	∆ costs (B-A)	В	∆ effects (B-A)	$\Delta \text{ costs}/\Delta$ effects for treatment B vs treatment A
C	C	∆ costs (C-B)	С	∆ effects (C-B)	$\Delta \text{ costs}/\Delta$ effects for treatment C vs treatment B

3.3 Estimation of costs

3.3.1 Costs and frequency of use of services and costs

. When participants consent to enter the study, the researchers randomly allocate them into one of the three trial arms. Each of the three arms is associated with a different cost. For the within-trial analysis, we will base these costs on the interventions and healthcare services used during the 12-month follow-up period post-randomisation.

3.3.2 Costs of Interventions

Three management strategies are being evaluated as part of this study are:

- Conservative management only (non-pharmacologic treatments)
- Conservative management plus Fludrocortisone
- Conservative management plus Midodrine

Conservative management costs

We will base each form of conservative management on the data collected within the electronic case report form (e-CRF) and estimate it on an individual-participant level (micro-costing). The costs of conservative management will be a sum of every aspect, considering the mix of staffing overheads, disposable equipment, and reusable equipment.

The estimation of these costs will utilise the dummy tables presented in the Appendix, specifically Table 5.1.

We will record the length of time and the number of intervals for the conservative management interventions. The staff costs will consist of the grade of the health care professional per hour. These costs have arisen because health professionals' numbers, types, and grades will be assumed based on consultations with the research team. Total staff costs will be calculated by multiplying the cost per session by the number of sessions within a particular time horizon. The costs per session would be derived by multiplying the duration of a session in minutes by the cost of staff per minute. The cost of staff per minute will be gathered from the Unit costs of health and social care ⁽¹⁵⁾. Total staff costs will allow for the average expenses per patient per arm. The total overhead costs will be calculated by multiplying the costs per session by the number of sessions. The costs of overheads will be retrieved from the Unit costs of health and social care ⁽¹⁵⁾.

The research team will need to confirm what reusable and consumable equipment is required for each type of conservative management. First, the cost per session will be multiplied by the number of sessions to calculate the total disposable equipment costs. Next, the disposable equipment used will be multiplied by the cost per item to calculate the total equipment costs. The cost per item would be sourced from the NHS Supply Chain website ⁽¹⁶⁾. Finally, the number of reusable equipment used in a session will be multiplied by the cost per item, which will then be multiplied by the number of times equipment can be used, the life span in years, and the discount rate. This multiplication will be multiplied by the number of sessions to calculate total reusable costs.

NHS tariffs for conservative intervention will be used in sensitivity analysis, and the results compared to the micro-setting will be estimated using the methods described above.

Cost of Fludrocortisone

As described above, individuals will receive a starting dose of 10m micrograms daily; frailer patients may receive a starting dose of 50 micrograms. This decision will be based on the discretion of the clinician. Clinicians will be encouraged to titrate towards the highest clinically effective dose. As suggested by the British National Formulary (BNF), the highest dose used within this trial is 400 micrograms; however, most sites will use the maximum dose of 300 micrograms as this is the usual practice. The dummy tables used to estimate these costs are shown in the Appendix, Table 5.2.

The unit costs of the Fludrocortisone will be derived from the BNF ⁽¹⁷⁾. The BNF documents the costs per pack of Fludrocortisone and the number of tablets in a pack allowing for the cost per tablet to be calculated by dividing the number of tablets by the cost per pack. The number of tablets used per dose will be calculated by dividing the dose from the protocol by the mass of the tablet. The cost per tablet will be multiplied by the number of tablets used per dose to calculate the total daily costs. Total costs will be calculated by multiplying the total cost per day by the time horizon in days.

- cost per tablet = cost per pack/number of tablets in a pack
- number of tablets used per dose = dose from protocol/ mass of tablets
- total costs per day = cost per tablet X number of tablets used per dose
- total costs = total costs per day X by time horizon in days

In addition, the costs of the clinicians administering the therapy can be identified in the Unit costs of health and social care and NHS tariffs ^(15, 18). The staff costs for administering the medication will be getting the grade of the staff, which the research team will confirm. The hourly rate of this staff will be retrieved from the Unit cost of health and social care. The research team would estimate the mean time required to administer Fludrocortisone. Staff costs per session will be calculated by dividing the

hourly staff rate by the time needed to help with the medication. Total staff costs will be calculated by multiplying staff costs per session by the number of sessions.

The estimates of the unit costs of Fludrocortisone will be added to the staff costs of administering. Total costs will be calculated for each participant, and an average cost per arm will be summarised as the average total resource use and total intervention cost per arm.

Cost of Midodrine

Participants who are randomised to Midodrine with conservative management will typically receive a starting dose of 2.5mmg TDS orally. Depending on the discretion of the clinician, lower doses and frequencies may be accepted. The maximum dose in this study is 10 mg. The costs of Midodrine will be estimated by the same method used for Fludrocortisone explained in the paragraph above, and the unit cost can be found in the BNF ⁽¹⁹⁾. The dummy tables used to estimate these costs are shown in the Appendix, Table 5.2.

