6.1.1.2 Overheads

Overhead type	Unit cost	Cost per session*	Number of sessions*	Total overhead costs*	Note
Туре	Cost per minute				
Room cost					
Heat power and light					
Internet					
Print outs					
Totals					

* These are calculated

6.1.1.3 equipment disposable

Equipment item		Cost per item	Cost per session*	Number of sessions	Total Equipment
Туре	Number used				costs*
Equipment 1					
Equipment 2					
Totals					

6.1.1.4 equipment reusable

Equipment item/Type	Number used	Number of times equipment can be used	Lifespan (years)	Discount rate	Cost per item per use	Cost per session*	Number of sessions*	Total reusable Equipment costs*
Equipment 1								
Equipment 2								
Totals								

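### The reusable-equipment costing rule multiplies price by uses, lifespan and discount rate where it should annuitise and divide by uses, so it cannot yield the per-use cost in the SAP's own tables

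*SAP*

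**What the plan says.** SAP section 3.3.2, under conservative management costs, sets the reusable-equipment cost in three steps.

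- Step 1: "the number of reusable equipment used in a session will be multiplied by the cost per item".
- Step 2: that product is taken, "which will then be multiplied by the number of times equipment can be used, the life span in years, and the discount rate".
- Step 3: "This multiplication will be multiplied by the number of sessions to calculate total reusable costs".

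The product of steps 1 and 2 therefore serves as the cost per session.

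The same section sends the analyst to the appendix dummy tables. Each of the six reusable-equipment tables (6.1.1.4, 6.1.2.4, 6.1.3.4, 6.1.4.4, 6.1.5.4 and 6.1.6.4) has columns for "Number of times equipment can be used", for lifespan in years and for "Discount rate". These are followed by "Cost per item per use", a cost per session and a total. All cells are blank.

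Section 2 says that recruitment fell short and the trial closed early, so that section 3 records the within-trial analysis as first planned and section 4 governs. Section 4.2 drops the complete within-trial evaluation. It keeps descriptive statistics on completion rates, resource use and EQ-5D-5L, and adds an early economic model with value-of-information methods.

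**The concern.** The cost of using a durable item once is its price spread over the uses it delivers, with an allowance for the capital tied up. Uses must therefore enter as a divisor, and lifespan and discount rate must enter through an annuity factor. In section 3.3.2 all three enter as multipliers, and nothing in the rule divides.

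Three consequences need no outside figure. An item that can be used more often costs more per session. An item that lasts longer costs more per session. At a discount rate of zero the item costs nothing.

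Text and tables also disagree. A per-use cost comes from spreading the price over the uses, and the text never derives one. An analyst cannot follow both.

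At stake is the conservative-management cost, which is a component of all three strategies. Section 3.3.2 is the only written rule for it, and section 4 puts no other in its place.

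**Working it through.** **Inputs.** The SAP states no reusable-equipment cost, so there is no figure to reproduce. It gives no value for price P, uses U, lifespan L or discount rate r. For the price, it says of disposable items that "The cost per item would be sourced from the NHS Supply Chain website"; I take cost per item to mean purchase price for reusable items too. It does not say whether U is counted per year or over the item's life. All values below are assumptions.

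**Rule as written**, for n items per session:

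n × P × U × L × r

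**Comparator.** Annuity factor AF = (1 − (1+r)^−L) / r. Equivalent annual cost = P / AF. With U as lifetime uses, uses per year = U / L, so the cost per session is

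n × (P / AF) × L / U

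**Ratio of the two.** P, n and L cancel, leaving U² × r × AF = U² × (1 − (1+r)^−L).

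**Numbers.** Take r = 3.5%, L = 5 years, P = £50 and n = 1.

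- 1.035^−5 = 0.8420, so AF = 0.1580 / 0.035 = 4.515.
- Equivalent annual cost = 50 / 4.515 = £11.07.
- At U = 100, the rule gives 50 × 100 × 5 × 0.035 = £875.00.
- At U = 100, the comparator gives 11.07 / 20 = £0.55.

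| Lifetime uses U | Rule as written | Annuitised, per use | Ratio |
|---|---|---|---|
| 2 | £17.50 | £27.69 | 0.63 |
| 10 | £87.50 | £5.54 | 15.8 |
| 50 | £437.50 | £1.11 | 395 |
| 100 | £875.00 | £0.55 | 1,580 |
| 200 | £1,750.00 | £0.28 | 6,321 |

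**Where the direction turns.** The ratio is 1 at U = 1 / √(1 − (1+r)^−L). At 3.5% this is about 5.4, 3.9, 2.5 and 1.9 uses for lifespans of 1, 2, 5 and 10 years. Below those numbers the rule understates the cost.

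**Range.** Over r from 1.5% to 5%, L from 1 to 10 years and U from 1 to 1,000, the ratio runs from about 0.01 to about 386,000 with U as lifetime uses. With U as uses per year it is L times larger, up to about 3.9 million.

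**Other readings of the text.**

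- Straight-line spreading, P / U, in place of an annuity: the ratio is U² × L × r, which at U = 50 and L = 5 is 437.5. The conclusion does not depend on annuitising.
- Discount rate read as a discount factor, (1+r)^−L, at 3.5%: the ratio is U² × AF × (1+r)^−L, about 177 at L = 2 and U = 10, and about 38,000 at L = 5 and U = 100. This does not rescue the rule.

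**The case against.** The best defence is that this is loose prose. Section 3.3.2 says the dummy tables will be used, and their per-use column points to the intended method. The fludrocortisone text in the same section has a similar slip, describing cost per tablet as tablets divided by pack cost; the formula list below it and the worked rows in Appendix 6.2.2 put that right. Reusable equipment, however, has no formula list and no worked row, so nothing corrects the sentence. The low and high values in section 3.5.2 come from confidence limits around the same cost and cannot show an error of form. The NHS-tariff comparison in section 3.3.2 might expose an absurd figure but would not repair the base case.

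The defence on consequence is stronger. The analysis that this costing served has been withdrawn, and none of the four descriptive analyses in section 4.2 costs conservative management. That stands.

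A reader might infer three further things that the document does not support:

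- **Costs are hundreds or thousands of times too high.** The inputs are blank, and for items used very few times the rule gives too low a cost.
- **The error will swamp the other costs.** The research team has still to confirm which equipment is needed, and the tables name none. Compression hosiery, for instance, has blank tables for both disposable and reusable items. Where use is the same in every arm, the error cancels in increments.
- **The rule feeds the early economic model.** Section 4.2 names trial data, literature and expert opinion as sources and does not mention these micro-costs. The link is plausible but not stated.

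**Conclusion.** The point holds as an error in the form of the rule and as a conflict between section 3.3.2 and the reusable-equipment tables. It is a wrong rule, not missing detail, and that conclusion rests on no assumed figure.

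The size does rest on assumptions. At 3.5% and 5 years with uses counted over the item's life, the ratio to a proper per-use cost is about 0.6 at 2 uses, 16 at 10, 395 at 50 and 6,300 at 200. These are illustrations, not estimates for this trial.

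The consequence is conditional. It arises if the micro-costs are reported, or if they enter the early economic model. In the model, incremental results would be distorted where equipment use differs between strategies; where use is equal, only the cost levels would be wrong.

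**What to change.** Replace the reusable-equipment sentence in section 3.3.2 with:

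- equivalent annual cost = price × r / (1 − (1+r)^−L);
- cost per item per use = equivalent annual cost / uses per year, where uses per year = lifetime uses / L if uses are counted over the lifespan;
- cost per session = items used × cost per item per use;
- total = cost per session × number of sessions.

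State the discount rate. Define the number of uses as annual or lifetime, because the choice changes the result by a factor of L. Add a purchase-price column to the six reusable-equipment tables. They have no uses-per-year column either, so add one or state the conversion from lifetime uses.

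If these micro-costs will not be reported or used in the early economic model, it is enough to mark the rule as superseded in section 4.2.

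The cost is a short text edit and a small change repeated in six tables. Price, uses, lifespan and rate are inputs that the present rule already calls for.

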To identify the primary inputs that could be changed to make Fludrocortisone and Conservative Management more or less cost-effective relative to both Midodrine and Conservative Management and Conservative Management alone.

Intervention costs

Conservative management

As mentioned before, we will use micro-costing to calculate conservative cost management. We will use sensitivity analysis to explore how low and high estimates affect the ICER. In addition, we will also investigate how the type of conservative management can influence the ICER separately. This form of analysis will be achieved by one-way sensitivity analysis. We will use higher and lower values of the intervention cost using a 95% confidence interval. Multiway sensitivity analysis will allow us to assess the impact of variation in the costs of Fludrocortisone and Midodrine.

Fludrocortisone and Midodrine

As mentioned, certain assumptions about the pharmacological interventions, such as the dose strength and the number of tablets used in a day, will be tested using sensitivity analysis. In the sensitivity analysis, we will explore the effect of each medication's high and low estimations on the ICER.

Cost of services

As mentioned previously, the assumptions about the cost of services would be assessed using sensitivity analysis. This analysis will determine non-NHS, private healthcare, and social care resources. For each cost, we will investigate the effect of using higher and lower cost estimates on the cost-effectiveness results, and whether the ICER goes above or below the threshold. Results from the sensitivity analysis will be presented using a tornado diagram for multiple one-way sensitivity analyses for higher and lower values of service cost.

Utility values

We will use EQ-5D-5L crosswalked to the EQ-5D-3L value set in the base case analysis ⁽³¹⁾. In sensitivity analyses, we will use alternative crosswalk algorithms (e.g., provided by van Hout et al.) and the population value set for the EQ-5D-5L to investigate the effect of these utility values on the ICER⁽³⁸⁾.

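### The drug-cost rule prices one protocol dose over the whole time horizon, so upward titration, and stopping for reasons other than an adverse event, never enter a participant's drug cost

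*SAP*

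**What the plan says.** The rule for fludrocortisone stands in section 3.3.2 (Cost of Fludrocortisone) as a chain of formulas. The dose term is "number of tablets used per dose = dose from protocol/ mass of tablets" and the duration term is "total costs = total costs per day X by time horizon in days". Section 3.3.2 (Cost of Midodrine) carries the method over: "The costs of Midodrine will be estimated by the same method used for Fludrocortisone".

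Appendix table 6.2.2 fills the rule in for fludrocortisone with three rows (100, 50 and 300 micrograms). Each has 365 days, including the 50 microgram row that is labelled a starting dose. The midodrine table, 6.2.4, is blank and has a column for number of days.

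Four other statements bear on the rule:

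- Section 3.3.1: "we will base these costs on the interventions and healthcare services used during the 12-month follow-up period post-randomisation".
- Section 3.3.2, on fludrocortisone: "Total costs will be calculated for each participant, and an average cost per arm will be summarised".
- Section 3.3.2, on dosing: "Clinicians will be encouraged to titrate towards the highest clinically effective dose", and "the highest dose used within this trial is 400 micrograms".
- Section 3.3.6 (Adverse Events): if an adverse event leads to a dose reduction, the cost inputs change from the resolution date. If it leads to withdrawal of the drug, only conservative management is costed from that date.

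Section 3.5.2 says that assumptions about the drugs, "such as the dose strength and the number of tablets used in a day, will be tested using sensitivity analysis".

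**The concern.** The base rule contains no term for a participant's recorded dose or days on drug. It also names no data source for exposure, whereas the same section costs conservative management from the electronic case report form for each participant. Yet the plan expects doses to rise after the start, and people can stop a drug for lack of effect, by choice or through death. None of these enters the cost unless an adverse event caused the change.

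Drug cost is the component that the two active strategies have and the control strategy lacks. An error in it goes straight into their incremental cost against control, and it need not be equal for two drugs with different dose ranges. A near-constant drug cost would also remove real variation between participants from the bootstrap planned in section 3.5.2. After early closure, the remaining routes are the resource-use summaries by group and the early economic model with its value-of-information calculation (section 4.2).

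**Working it through.** **Inputs.** From table 6.2.2: £8.06 per pack, 30 tablets per pack, 100 micrograms per tablet, 365 days. From section 3.3.2: the formulas quoted above.

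**Step 1: reproduce the plan's figures.** Cost per tablet = 8.06 / 30 = £0.26867. Cost = 0.26867 × (dose / 100) × 365.

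| Daily dose | Calculation | Result | Table 6.2.2 |
|---|---|---|---|
| 100 micrograms | 0.26867 × 1 × 365 | £98.06 | £98.06 |
| 50 micrograms | 0.26867 × 0.5 × 365 | £49.03 | £49.03 |
| 300 micrograms | 0.26867 × 3 × 365 | £294.19 | £294.19 |

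All three agree, so the table applies one constant dose for 365 days. The same formula at 400 micrograms gives 0.26867 × 4 × 365 = £392.25. The table has no row for this dose and calls 300 micrograms the maximal dose, while sections 3.1 and 3.3.2 give 400 as the highest in the study. Section 3.3.2 adds that most sites will use a maximum of 300.

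**Step 2: cost by dose period.** Drug cost = sum over dose periods of (tablets per day × cost per tablet × days). The SAP gives no titration schedule and no exposure data. The courses below are assumptions chosen to show the range; they are not proposed schedules.

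- *Titrated:* 100 micrograms for 28 days, 200 for 28, 300 for 309. Tablets = 28×1 + 28×2 + 309×3 = 1,011. Cost = 1,011 × 0.26867 = £271.62.
- *Low start:* 50 micrograms for 28 days, then 100 for 337. Tablets = 28×0.5 + 337 = 351. Cost = £94.30.
- *Stopped at day 60, no adverse event, 100 micrograms:* 60 × 0.26867 = £16.12.

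**Step 3: compare with the fixed rows.** The plan does not say which row a participant is assigned, so each plausible row is shown.

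| Assumed course | Cost by dose period | Row charged | Error |
|---|---|---|---|
| Titrated to 300 | £271.62 | 100 row, £98.06 | 98.06/271.62 = 0.36, so 64% too low |
| Titrated to 300 | £271.62 | 300 row, £294.19 | 294.19/271.62 = 1.08, so about 8% too high |
| 50 then 100 | £94.30 | 50 row, £49.03 | 49.03/94.30 = 0.52, so 48% too low |
| 50 then 100 | £94.30 | 100 row, £98.06 | 98.06/94.30 = 1.04, so 4% too high |
| 100, stopped day 60 | £16.12 | 100 row, £98.06 | 98.06/16.12 = 6.1 times |

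**Step 4: scale.** The largest gap in this table is 271.62 − 98.06 = £173.56 per participant. At the £20,000 per QALY threshold in section 3.5, that equals 173.56 / 20,000 = about 0.009 QALY.

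**Midodrine.** The SAP gives no price and table 6.2.4 is empty, so no figure can be computed.

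**The case against.** The case on the other side has five parts.

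- *Adverse events are covered.* A reader might infer that drug cost reflects neither dose nor time on drug for anyone. The SAP does not support that. Section 3.3.6 (Adverse Events) makes both specific to the participant when an adverse event leads to reduction or withdrawal. This stands, and it limits the point to upward titration and to stopping for other reasons.
- *The 365 days is not in the rule.* The formula says only time horizon in days; 365 appears in the fludrocortisone dummy table alone. This stands, and no 365-day charge is stated for midodrine. Still, a time horizon is not time on drug, and the only worked table uses the full year.
- *The direction is not fixed.* It is tempting to say that the rule understates cost for titrated participants. That holds only if they are charged the row they started on. Charged the row they reached, they are slightly overcosted. This stands; the missing assignment rule is itself part of the defect.
- *The analysis has been dropped.* The end of section 2 calls section 3 the originally planned analysis, and section 4.2 no longer proposes a complete within-trial evaluation. Nothing says that the descriptive summaries or the early model will use this formula. The remark in section 4.2 about insufficient 12-month data concerns the EQ-5D-5L level mapping, not drug exposure. This stands and lowers the weight. The point does not vanish, because section 4.2 still reports resource use by group and uses trial data in the early model, and no other drug-costing rule is given.
- *The sums are small and already varied.* Section 1 calls the cost of medication modest, and section 3.5.2 varies dose strength and tablets per day. Both are true. But varying an assumed dose does not replace the observed dose, and the drug sensitivity analyses do not mention duration.

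**Conclusion.** The rule is wrong as written, with limited impact. Followed literally, it gives the wrong drug cost for any participant who is titrated upwards, or who stops for a reason other than an adverse event. That conflicts with the commitments in sections 3.3.1 and 3.3.2 to cost what was used, participant by participant.

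Under the assumed fludrocortisone courses, the error runs from 64% too low to about six times too high. Its sign for titrated participants depends on a row assignment that the plan does not state. In money, it reaches £173.56 per participant in these examples. The figures rest on the price in table 6.2.2 and on dose courses that are assumptions. They do not show an average error by arm, and nothing can be said about the size for midodrine. Nor does the SAP show that any participant will in fact be charged for 365 days in the close-down analyses.

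**What to change.** In section 3.3.2, replace the last two formulas and carry the change to midodrine: drug cost per participant = sum over that participant's recorded dose periods of (tablets per day at the dose in force × cost per tablet × days on that dose). End the sum at the earliest of drug stop, death, withdrawal or end of observed follow-up.

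Then:

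- Name the data source for dose and dates. The SAP does not describe one for the drugs, so the sponsor should confirm what was recorded.
- Keep the fixed-dose rows of tables 6.2.2 and 6.2.4 as sensitivity scenarios, or as the fallback where dates are missing, and state how a row is then assigned.
- In close-down analysis 2 (section 4.2), summarise dose-days by arm, and use that observed exposure for any trial-based drug cost in the early economic model.
- Reconcile sections 3.3.1, 3.3.2 and 3.3.6 (Adverse Events) with table 6.2.2. Include the 300 microgram maximum in the table against the 400 micrograms in sections 3.1 and 3.3.2. Which figure applies is for the sponsor to settle.

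The cost is a change of wording and some extra data handling. The adverse-event section already costs from dated changes, so this extends an approach that the plan accepts. The drawback is reliance on the completeness of recorded dose dates, which the fallback covers.
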